4.2. Safety Endpoints

The following safety data will be collected and summarized according to the study protocol:

- Adverse events
- Laboratory test data
- Vital signs data
- Electrocardiography (ECG)
- Physical examination

4.2.1. Adverse events

Including any AE occurring after signing the informed consent form (ICF) and being enrolled in the study.

Any AE occurring after the treatment or occurring prior to the treatment but worsening after the treatment will be considered as a treatment-emergent AE (TEAE). Including but not limited to the followings:

- Worsening of pre-existing (prior to start of study treatment) medical conditions/diseases after the start of investigational drug administration.
- Any new AE occurring after the start of study treatment.
- Clinically significant abnormal laboratory findings or results occurring after the start of study treatment.

If an event occurs during non-treatment period (e.g., treatment interruption or follow-up period after treatment discontinuation), then this event will still be considered to be treatment emergent and attributed to previous therapy.

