- [15] Tumor FDG-PET examination: Perform on D1 (± 7 days) of Weeks 17 and 25 after the start of treatment. For subjects who have not obtained two negative FDG-PET results after Week 1 and until Week 49, it is necessary to add a tumor FDG-PET examination on D1 (± 7 days) of Week 49. If it is necessary to determine whether a radiographic CR is obtained at other unscheduled FDG-PET evaluation time points after the start of treatment, the FDG-PET evaluation must be performed within 4 weeks after the CT evaluation.

- [16] Bone marrow aspiration and biopsy: The subject can start the study treatment before obtaining the bone marrow biopsy result, but the result must be recorded in the subject's CRF. Patients with bone marrow involvement at baseline require bone marrow aspiration or biopsy to confirm CR status. Bone marrow aspiration and biopsy specimens are collected within 2 weeks after the CT scan. There is no need to perform bone marrow assessment after the bone marrow aspiration and biopsy result turns negative.
- [17] B symptom assessment: including pyrexia of > 38 °C of unknown cause; night sweats; weight loss of > 10% within 6 months before the assessment. The evaluation will be conducted on D1 of Cycle 1, and every 2 cycles thereafter until the discontinuation of study treatment. In addition, the evaluation is performed when the subject obtains PR or CR for the first time; if the subject has obtained PR before CR, the evaluation should be performed again when CR is obtained.
- [18] Concomitant medication: Concomitant medications from 14 days before study treatment to 90 days after the last dose of study treatment will be collected. After the last dose, only concomitant medications for treatment-related AEs will be recorded.
- [19] AE: As per NCI CTCAE V4.03, all AEs that occur from the signing of the informed consent form to 90 days after the last dose or the start of new anti-tumor treatment should be observed and documented. From 30 days after the last dose, for non-serious AEs, only those related to the investigational drug, including AEs of special interest, will be collected. All AEs should be followed up until Grade 0-1, recovery to baseline levels, or reasonably explained (e.g., lost to follow-up or death).

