10. ADVERSE EVENT REPORTING

10.1. Adverse Event (AE)

10.1.1. Definition of adverse event

An AE refers to any untoward medical occurrence in a clinical investigation subject administered a pharmaceutical product and which does not necessarily have to have a causal relationship with this treatment. In this study, all AEs occurring from signing the informed consent form to 90 days after the last dose will be collected. From 30 days after the last dose, for non-serious AEs, only those related to the investigational drug will be collected.

AEs can include any unfavorable and unintended symptoms, signs, laboratory abnormalities, or diseases, including the following:

- 1) Worsening of pre-existing (prior to entering clinical study) medical conditions/diseases (including worsening symptoms, signs, or laboratory abnormalities);
- 2) Any new AE: Any new adverse medical conditions (including symptoms, signs, and newly diagnosed diseases);
- 3) Clinically significant laboratory abnormalities.

All AEs should be collected in detail by the investigators, including: the name of the AE and description of all relevant symptoms, onset time, severity, correlation with the investigational drug, duration, measures taken, as well as final results and outcomes.

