10.1.3. Determination of the relationship between AEs and investigational drug

AEs will be collected from the signing of the informed consent form to 90 days after the last study dose or the start of new anti-tumor treatment, regardless of whether the event is related to the investigational drug or whether any medication is taken against the AE. From 30 days after the end of treatment, for non-serious AEs, only those related to the investigational drug will be collected. Any discomforts complained by the subject or changes in objective laboratory measurements during the treatment period should be faithfully recorded. The severity, duration, measures taken, and outcome of AEs should also be documented. The study physician should comprehensively assess the relationship between the AE and the investigational drug by considering the temporal relationship between the administration of investigational drug and the occurrence of AE, the characteristics of the investigational drug, the toxicological and pharmacological effects of the investigational drug, concomitant medications, underlying

diseases, medical history, family history, as well as dechallenge and rechallenge. The causality assessment will be provided using the following five categories: "related, possibly related, unlikely related, not related, and unassessable". Events that are assessed to be "related", "possibly related", and "unassessable" will be listed as adverse drug reactions. When calculating the incidence of AEs, the total of these three categories will be used as the numerator and the total number of subjects for safety assessments will be used as the denominator.

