10.2.5. Other anti-tumor treatment

SAEs should be collected from the signing of the informed consent form until 90 days after the last dose of the investigational drug. Within 90 days after the last dose, SAEs that occur after the start of new anti-tumor treatment should also be reported.

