5.5.2. Adverse events

TEAE is any adverse event after treatment with the investigational drug. AEs will be summarized using descriptive statistics according to Hengrui's Statistical Analysis Reporting Standards, including but not limited to:

- Overview of AEs (of all causes and treatment-related);
- Summary of SAEs;

- Incidence and severity of AEs (of all-cause and treatment-related);
- Causality assessment of AEs;
- Analysis of adverse events of special interest (AESIs).

AESIs mainly include the following:

- Haemangioma (time to onset and duration)
- Grade ≥ 3 infusion reaction
- Grade ≥ 2 diarrhoea/colitis, uveitis, interstitial pneumonia
- Grade ≥ 3 other immune-related adverse events: skin, digestive tract, lungs, endocrine (by system organ class)
- Hepatic enzyme abnormalities: ALT, AST and total bilirubin are abnormal against baseline
- Grade 4 amylase or lipase increased.

For AEs occurring after the start of study treatment, treatment-related AEs include those whose causality with the investigational drug is related, possibly related, unlikely related, or unassessable; if the causality assessment is missing, then the AE will be deemed treatment-related for analysis.

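### The SAP's treatment-emergent rule has no end date and no cut at new anti-tumour therapy, so SAEs arising on a later regimen enter the SHR-1210 all-cause counts

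*SAP*

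**What the plan says.** SAP 4.2.1 opens the category with "Any AE occurring after the treatment or occurring prior to the treatment but worsening after the treatment" and gives no closing date. It then turns to events during a treatment interruption or in follow-up after discontinuation: "then this event will still be considered to be treatment emergent and attributed to previous therapy". SAP 5.5.2 repeats the open rule: "TEAE is any adverse event after treatment with the investigational drug". Neither section mentions new anti-tumour therapy. Protocol 12.5.5 uses the term TEAE without defining it, so the SAP rule is the only one in the two documents.

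The protocol's collection windows are narrower and differ by type of event:

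- **All AEs.** Note 19 to the Schedule of Activities says that AEs from consent "to 90 days after the last dose or the start of new anti-tumor treatment should be observed and documented". Sections 8.4 and 10.1.3 give the same limits. Section 10.1.1 gives day 90 without mentioning new therapy.
- **Non-serious AEs.** Section 10.1.1 says: "From 30 days after the last dose, for non-serious AEs, only those related to the investigational drug will be collected". Note 19 and Section 8.4 use the same anchor. Section 10.1.3 uses another: "From 30 days after the end of treatment, for non-serious AEs, only those related to the investigational drug will be collected".
- **SAEs.** Section 10.2.5 collects them to day 90 and adds that, within that period, "SAEs that occur after the start of new anti-tumor treatment should also be reported". Section 10.2.6 accepts SAEs after day 90 only if they are suspected to be related to the drug.

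**The concern.** A treatment-emergent rule should cover a period in which events are collected in one way and in which the study drug is a plausible contributor. This rule does neither after the last dose.

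First, a subject who moves to another regimen within 90 days can have an SAE on that regimen, and the SAP counts it as emergent on SHR-1210. In a single-arm trial no control arm shows how much of the SAE rate comes from later treatment.

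Second, the all-cause non-serious tables pool a period of full capture with one in which unrelated events are not recorded. That tilts the late mix toward related events.

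Third, the attribution wording sits beside a separate causality assessment and invites confusion between timing and cause.

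**Working it through.** The plan states no figure on this point, so the check sets the SAP rule against what the protocol collects. The wording of the outer limit does not say which of day 90 and new therapy governs; it is read here as the earlier of the two.

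| Period after last dose | Non-serious, unrelated | Non-serious, related | SAE | Status under SAP 4.2.1 and 5.5.2 |
|---|---|---|---|---|
| To day 30, no new therapy | Collected | Collected | Any cause | TEAE |
| After day 30 to day 90, no new therapy | Not collected | Collected | Any cause | TEAE |
| To day 90, after new therapy starts | Not collected (10.1.1 does not state this cut) | Not collected (same caveat) | Any cause (10.2.5) | TEAE |
| After day 90 | Not collected | Not collected | Only if suspected related (10.2.6) | TEAE |

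**Step 1: SAEs after new therapy.** Row 3 is the main gap. On the reading used, SAEs are the only events still collected there, and the SAP places them in the all-cause TEAE and SAE summaries with no separate category.

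**Step 2: treatment-related tables.** SAP 5.5.2 builds these from the causality category and counts related, possibly related, unlikely related, unassessable and missing. Protocol 10.1.3 counts only related, possibly related and unassessable as adverse drug reactions. A row 3 SAE judged not related stays out of the treatment-related tables. One judged unlikely related goes in under the SAP, but would not under the protocol.

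**Step 3: mixed capture of non-serious events.** Selective capture lasts 90 − 30 = 60 days, and 60/90 = 67% of the post-dose window. As an illustration only, assume a constant rate of non-serious events over days 0 to 90, no new therapy, and a share s of events judged related. The captured fraction is (30 + 60s)/90:

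- s = 0.10: 36/90 = 40%
- s = 0.30: 48/90 = 53%
- s = 0.50: 60/90 = 67%

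The documents give no value for s. The calculation does not apply to SAEs, whose planned capture is all-cause to day 90.

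**Step 4: the anchor.** Note 6 to the Schedule of Activities provides for discontinuation more than 84 days after the last dose; Section 8.4 gives 42 days for the same provision. If end of treatment in 10.1.3 means the discontinuation date, the 30-day point falls beyond day 84 + 30 = 114 or day 42 + 30 = 72 after the last dose. The first lies past the 90-day limit. The two anchors are therefore not interchangeable.

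**The case against.** The strongest reply is that the protocol already bounds the rule. SAP 4.2 says safety data are collected and summarised according to the protocol. Non-serious collection ends by day 90, or at new therapy where that cut is stated, and unrelated SAEs end at day 90. Only suspected-related SAEs are open-ended, and those belong in a safety summary. This stands: a reader might infer an unlimited TEAE count, and the documents do not support that. It does not answer row 3, where the protocol itself supplies the SAEs.

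A reader might also infer that the attribution sentence makes every follow-up event drug-related in the tables. It does not. The phrase says previous therapy, most naturally the study treatment given before the interruption or discontinuation, and the related tables use the causality category. Nor does all AE capture become partial after day 30; the restriction covers non-serious events only.

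A numerical estimate is tempting too. One could take the complement of the 65% design ORR, 0.35 × 60 = 21 subjects, assume that all start new therapy within 90 days and that 10% to 30% have an SAE on it, and obtain 2.1 to 6.3 subjects, or 3.5 to 10.5 percentage points. The documents do not support this. Non-response is not the start of new therapy: treatment runs until progression, and Section 8.6 allows it beyond progression. The SAE rate has no source. A subject with an earlier SAE adds nothing to a subject-level rate. If only half of the 21 switched, the range would be 1.75 to 5.25 points; if instead 30% of the 21 already had an SAE, it would be 2.45 to 7.35. Sections 10.2.2 and 10.2.3 also exclude some events from SAE status, such as admission solely for blood products and non-fatal consequences of progression.

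Two further points carry weight. Protocol 7.1.6.1 warns that immune-related events can appear months after dosing stops, so an inclusive window is defensible and a day-30 cut alone would lose information. The sponsor's reporting standards, cited in SAP 5.5.2, are not available and might set a window, although one set there would conflict with the SAP's open-ended text.

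**Conclusion.** The point holds for descriptive safety reporting. Followed as written, the plan counts SAEs arising on a subsequent regimen in the SHR-1210 all-cause TEAE and SAE summaries, and puts those judged unlikely related in the treatment-related tables as well. All-cause non-serious TEAE rates mix full capture with selective capture.

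The size cannot be derived, because the documents give neither the number of subjects who will start new therapy within 90 days nor their SAE rate on it. The direction for SAEs is clear: the counts can only be raised by these events.

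The ORR analysis and its decision rule are unaffected. The conclusion rests on reading previous therapy as the study treatment, and on the SAP text not being overridden by sponsor standards outside the two documents. The anchor mismatch in Protocol 10.1.3 is a minor wording point.

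**What to change.** In SAP 4.2.1 and 5.5.2:

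1. End the TEAE window at the earlier of the protocol's 90-day collection limit after the last dose or the start of new anti-tumour therapy.
2. Flag SAEs after new therapy, and suspected-related SAEs after day 90, and summarise or list them separately.
3. Delete the attribution to previous therapy, so that causality comes only from the recorded assessment.
4. Add a table of all-cause non-serious AEs to day 30 after the last dose, beside the main table.

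In the protocol, reconcile the last-dose anchor (note 19, Sections 8.4 and 10.1.1) with the end-of-treatment anchor (Section 10.1.3). The different lists of related categories in Protocol 10.1.3 and SAP 5.5.2 also need reconciling, but the four changes above do not depend on it.

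The cost is SAP wording, one derived flag and one added table. The Schedule of Activities already records subsequent anti-tumour treatment in follow-up, so no new data item is needed. The downside is that a few late events move from the main table to a separate summary or listing. They remain reported, and the 90-day limit keeps delayed immune-related events in the main table up to that day unless new therapy starts first.

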4.2.2. Laboratory test

Laboratory measurements including hematology, hepatic and renal function, urinalysis and fecal occult blood, blood electrolytes, coagulation function, and thyroid function will be collected at the visit time points specified in the study protocol.

4.2.3. Vital signs

Vital signs such as blood pressure, heart rate, body temperature, and respiratory rate will be collected at time points predetermined in the study protocol.

4.2.4. Electrocardiogram (ECG)

Heart rate, PR, and QTc will be collected at time points predetermined in the study protocol.

4.2.5. Physical examination

Physical examination includes general condition, head and face, skin, lymph nodes, eyes, ears, nose, throat, oral cavity, respiratory system, cardiovascular system, abdomen, reproductive-urinary system, musculoskeletal system, nervous system, mental state, and others. These data will be collected at protocol-specified visit/time points.

4.2.6. Other safety endpoints

Assessment of B symptoms, IPS score, and ultrasound ECG.

4.3. Pharmacokinetic Endpoints

Not included in this SAP. See "PK Statistical Analysis Plan" provided by the vendor.

4.4. Pharmacodynamic Endpoints

None. This study does not involve PD endpoints.

4.5. Other Endpoints

None.

5. STATISTICAL ANALYSIS

5.1. General Considerations

5.1.1. Analysis sets

This study will involve the following analysis sets or populations:

- **Informed Consent Set (ICS)**

All subjects who have signed the informed consent form.

- **Full Analysis Set (FAS)**

Eligible subjects who have received the investigational drug.

- **Per-Protocol Set (PPS)**

A subset of the FAS, defined as subjects in the FAS who have experienced no important protocol deviations.

- **Safety Set (SS)**

All enrolled subjects who have received the investigational drug and have post-administration safety evaluation. The SS is the primary analysis set for safety analysis.

Table 1. Analysis sets and corresponding endpoints.

Endpoint	Analysis Sets		
	FAS	PPS	SS
ORR (%)*	X	X	
TTR (Month)	X		
TTP (Month)	X		
PFS (Month)	X		
DoR (Month)	X		
DCR (%)	X		
OS (Month)	X		
Safety (AE, LAB, VS, ECG, and PE)			X

*: Assessed by the investigator and independent review committee, respectively.

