8.2. Treatment Period

All examinations and evaluations during the treatment period should be completed prior to the administration.

- ECOG PS: Perform within 72 h prior to each dose
- Physical examination: including height, weight, symptoms, and signs. Lymph node regions (for example, submandibular, cervical, supraclavicular, armpit, and groin) and abdominal organs (for example, liver and spleen) are checked within 72 h before each administration;
- Vital signs: including body temperature, blood pressure, heart rate, and respiratory rate; measure within 72 h before each administration;

- Blood HCG test: Only for women of childbearing potential (WOCBP); test within 7 days before the first dose, and at least once every 4 weeks (\pm 7 days) thereafter, regardless of the dosing cycle;
- B symptom assessment: including pyrexia of > 38 °C of unknown cause, night sweats, or weight loss of $> 10\%$ (the evaluation will be conducted on D1 of Cycle 1, and every 2 cycles thereafter until the discontinuation of study treatment);
- PK blood collection: In Cycle 1, within 0.5 h pre-administration and within 5 min and at 2 h (\pm 10 min) post-administration on D1, and on D8 (\pm 60 min). In Cycles 2, 4, and 6, within 0.5 h pre-administration and within 5 min post-administration on D1 (only for subjects participating in the PK study);
- Injection of SHR-1210:
- Adverse event
- Concomitant medication/treatment

The following relevant examinations must be completed pre-administration in Cycle 2 and subsequent cycles (complete within 72 h pre-administration):

- Hematology: RBC count, hemoglobin, platelet count, WBC count, neutrophil count, and lymphocyte count;
- Urinalysis: WBCs, RBCs, and urine protein; if urine protein $\geq 2+$, 24-h urine protein quantitation is required;
- Fecal occult blood;
- Hepatic and Renal Function: including ALT, AST, TBIL, ALP, BUN or serum urea level, creatinine, and albumin;
- Blood electrolytes: including K^+ , Na^+ , Ca^{++} , Mg^{++} , and Cl^- ;
- Coagulation function: When international normalized ratio (INR) is not available, prothrombin time (PT) will be used; once every 2 cycles;
- Thyroid function: including TSH, FT3, and FT; once every 4 cycles
- Fasting blood glucose;
- LDH;

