12.4. Analysis Populations

This study will involve the following analysis sets or populations:

- Informed Consent Set (ICS): all subjects who have signed the informed consent form.
- Full Analysis Set (FAS): eligible subjects who have received the investigational drug. The FAS is the primary analysis set for efficacy analysis other than the primary efficacy endpoint.
- Evaluable Set (ES):
a subset of the FAS, defined as subjects with at least one post-baseline efficacy evaluation in the FAS. The ES is the primary analysis set for the primary efficacy endpoint ORR
- Per-Protocol Set (PPS): a subset of the FAS, defined as subjects in the FAS who have experienced no major protocol deviations. PPS is the secondary analysis set for efficacy analysis.
- Safety Set (SS): all enrolled subjects who have received the investigational drug and have post-administration evaluable safety data. SS is the primary analysis set for safety analysis.
- PK Set (PKS): all enrolled subjects who have received the investigational drug and have post-administration evaluable PK data (concentration and/or parameters).

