5.5. Safety Analyses

All safety analyses will be conducted based on SS.

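### The Safety Set carries an undefined post-dose data condition that the FAS lacks, so a dosed subject with little or no follow-up can drop out of the safety and exposure tables

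*SAP*

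**What the plan says.** **Safety Set.** SAP 5.1.1: "All enrolled subjects who have received the investigational drug and have post-administration safety evaluation". Protocol 12.4, repeated in the synopsis: "all enrolled subjects who have received the investigational drug and have post-administration evaluable safety data". Both require something to exist after dosing. One asks for an evaluation, the other for evaluable data, and neither document defines its term.

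**FAS.** SAP 5.1.1: "Eligible subjects who have received the investigational drug". Protocol 12.4 has the same content. There is no post-dose condition.

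**Use of the Safety Set.** SAP 5.5: "All safety analyses will be conducted based on SS". This covers extent of exposure (SAP 5.5.1) as well as adverse events. SAP 5.2 also puts medical history and prior therapy on the Safety Set and leaves demographics and baseline characteristics on the FAS. For adverse event incidence, protocol 10.1.3 says that "the total number of subjects for safety assessments will be used as the denominator".

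**Missing data.** SAP 5.1.6 deals with dates and censoring and leaves all other missing data alone. No rule returns an excluded dosed subject to the Safety Set.

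**The concern.** The usual safety population is everyone exposed, because exposure is fixed at the first dose and nothing later can change it. Here membership depends on what is available afterwards. Subjects who leave very early are the most likely to fail the condition, and early departure need not be unrelated to how the drug was tolerated.

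Two consequences follow. First, tables that should share a denominator may not: a dose that was given could be missing from the exposure summary, and baseline tables could differ between demographics (FAS) and prior therapy (Safety Set). Second, the undefined terms leave someone to decide, after treatment and with treatment known, whether scanty data are enough. A subject with one brief contact and no recorded event might be kept under one wording and dropped under the other.

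**Working it through.** The plan gives no figure on this point, so there is none to reproduce. The check compares the definitions, asks who could fail the condition, and then sizes the effect.

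**1. Definitions side by side**

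| Condition | FAS (SAP 5.1.1) | Safety Set (SAP 5.1.1) | Safety Set (protocol 12.4) |
|---|---|---|---|
| Received drug | yes | yes | yes |
| Eligible | yes | not stated (enrolled) | not stated (enrolled) |
| Post-dose condition | none | safety evaluation | evaluable safety data |

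An eligible, dosed subject with nothing recorded after dosing is in the FAS and outside the Safety Set under either wording. The SAP expects such subjects in the FAS: Appendix 1.1 censors PFS at the first dose for a living subject with no post-baseline assessment.

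**2. Who could fail the condition**

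- Protocol 8.2 states: "All examinations and evaluations during the treatment period should be completed prior to the administration". Laboratory tests and ECG on treatment begin later: "The following relevant examinations must be completed pre-administration in Cycle 2 and subsequent cycles".
- Cycles last 14 days, so Cycle 2 starts at about day 1 + 14 = day 15 (±3 days). For a subject who stays on treatment, the first scheduled post-dose examination falls shortly before that dose. The only scheduled contacts earlier in Cycle 1 are the PK draws, in 12 subjects.
- A subject who stops before then should still have end-of-treatment examinations (protocol 8.3) and site visits about 30 and 90 days after the last dose (protocol 8.4). The condition therefore bites only when these do not take place: a subject who is lost, or who withdraws and refuses further contact.

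**3. Size**

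Inputs: N = 60 planned subjects (SAP 2.3), all assumed dosed; k = number of dosed subjects excluded; x = number of other subjects with a given event. The documents give no k, so a range of 1 to 3 is assumed. The excluded subjects are taken to have no recorded event.

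- All dosed: x / 60
- Safety Set as written: x / (60 − k)
- Ratio of the two: 60 / (60 − k)

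| k | Denominator | Ratio | x = 6 | x = 12 |
|---|---|---|---|---|
| 0 | 60 | 1.000 | 10.00% | 20.00% |
| 1 | 59 | 1.017 | 10.17% | 20.34% |
| 2 | 58 | 1.034 | 10.34% | 20.69% |
| 3 | 57 | 1.053 | 10.53% | 21.05% |

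With three exclusions a 10% rate moves by about half a percentage point and a 20% rate by about one. On this assumption, leaving the subjects out raises the reported rates slightly.

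**The case against.** The strongest reply is that the condition does almost no work. Protocol 10.1.1 says that "all AEs occurring from signing the informed consent form to 90 days after the last dose will be collected". The schedule of activities lists adverse event recording under its safety evaluation heading, and protocol 9.2.1 treats adverse events as part of the safety assessment. Anyone with a post-dose event on record therefore has safety data. Early leavers are meant to complete safety follow-up (protocol 5.5), and SAP 5.1.5 lets an unplanned visit stand in for a missed one. The subject who remains, with no post-dose record at all, adds nothing to any numerator. Nor would the exclusion be hidden: SAP 5.2.1 reports how many were treated and how many are in each set.

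Most of this stands. In particular, a reader might infer that a subject who dies before the Cycle 2 visit would disappear from the safety tables, turning a fatal event into none. The documents do not support that. Death is a serious adverse event (protocol 10.2.1), including death from progression (10.2.3), and the report must give severity, relationship and outcome (10.2.6). On the natural reading that meets either wording. A death in an eligible dosed subject also counts in overall survival on the FAS.

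Two things are left. Neither document actually says that such a record satisfies the condition. And although the later SAP wording no longer says *evaluable*, its replacement is just as undefined.

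**Conclusion.** The point holds as a minor one about definition. Membership of the Safety Set depends on undefined post-dose data, worded differently in the two documents, while the FAS carries no such condition. A dosed subject with little or no follow-up can be dropped from the adverse event denominators, the exposure summary and the medical history and prior therapy tables. The primary ORR analysis does not use the Safety Set and is unaffected.

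The effect on event rates is small: about 0.2 to 0.5 percentage points on a 10% rate for one to three exclusions. This assumes 60 dosed subjects and excluded subjects without recorded events. The mismatch with the FAS applies only to eligible subjects, because the FAS requires eligibility. The case for change rests on removing a judgement made after treatment and on keeping denominators consistent. It does not rest on a hidden safety signal.

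**What to change.** In the protocol synopsis, protocol 12.4 and SAP 5.1.1, define the Safety Set identically as all enrolled subjects who received at least one full or partial dose of SHR-1210, with no condition on post-dose data. Point the denominator in protocol 10.1.3 to that set by name.

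This costs one sentence in each place and needs no new data. The downside is a slight dilution of event rates if a subject without follow-up is added, as in 6/59 = 10.17% becoming 6/60 = 10.00%. A footnote giving the number of dosed subjects with no post-dose safety record would let the reader see it.
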